2.6.2 Statistical hypothesis, model, and method of analysis

The primary efficacy analysis was to be performed by testing the following hypothesis:

- $H_0: p \leq 0.10$ vs. $H_A: p > 0.10$

The estimated proportion \hat{p} of patients who restore B-cell aplasia within 12 months following re-infusion with tisagenlecleucel will be presented together with an exact 95% Clopper-Pearson confidence interval (CI).

The null hypothesis was to be rejected if the lower limit of the 95% CI was greater than 0.10, demonstrating improvement after re-infusion. The estimated number of patients who restore B-cell aplasia required to reject the null hypothesis (H_0) is 10 (See Appendix [Section 5.4](#)).

The primary analysis will not be conducted as planned due to not enough patients enrolled for a meaningful analysis, based on early termination of the study as described above and in [Section 4](#). Data for the primary objective will be listed only.

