## 5 Population

The target population consists of pediatric and adolescent young adult patients up to and including 25 years of age with B-cell ALL who have been previously infused once with tisagenlecleucel and have a loss of B-cell aplasia. Approximately 54 subjects will be enrolled to allow 49 subjects treated.

The investigator or designee must ensure that only subjects who meet all the following inclusion and none of the exclusion criteria at screening and prior to infusion are offered treatment in the study.

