| IRC | Independent Review Committee |
| LD | Lymphodepleting |
| LDH | Lactate Dehydrogenase |
| LLOQ | Lower Limit of Quantification |
| LPLV | Last Patient Last Visit |
| MedDRA | Medical Dictionary for Drug Regulatory Affairs |
| MRD | Minimal Residual Disease |
| ORR | Overall Remission Rate |
| OS | Overall Survival |
| PB | Peripheral Blood |
| PD | Pharmacodynamics |
| PK | Pharmacokinetics |
| PRO | Patient-reported Outcomes |
| PT | Preferred Term |
| qPCR | Quantitative Polymerase Chain Reaction |
| SAE | Serious Adverse Event |
| SAP | Statistical Analysis Plan |
| SAF | Safety Set |
| SCT | Stem Cell Transplant |
| SOC | System Organ Class |
| TEAE | Treatment Emergent Adverse Event |

TFLs Tables, Figures, Listings
WBC White Blood Cell
WHO World Health Organization

1 Introduction

This Statistical Analysis Plan (SAP) describes the primary statistical analysis according to the statistical methodology of the clinical trial protocol CCTL019BUS03 (version 1.0, release date 23-Jun-2020) along with any additional analyses, specifications, or deviations from the protocol. This SAP may be used as a first draft of Section 9.7 (Statistical methods planned in the protocol and determination of sample size) and Appendix 16.1.9 (Documentation of statistical methods) of the Clinical Study Report (CSR).

Determination of the sample size is specified in [Section 3](#).

In the original SAP, it was planned that the primary analysis would be conducted at the end of the study when all patients who were re-infused with tisagenlecleucel had completed a 12-month study period. For this analysis, all primary, secondary, [REDACTED] objectives were to be addressed including all variables outlined up to Month 12 and all available safety data. Separate SAP documentation was to be created for any ad-hoc interim analyses required for publication.

However, this study terminated early due a very low rate of enrollment, which made it no longer feasible to continue with the trial; which meant there was insufficient data to perform the planned statistical analyses so study data will be listed only. This SAP amendment was issued after the decision to terminate the study; therefore, the changes to planned analyses are reflected in this document (see [Section 4](#)).

This document is written in the future tense. It will be reviewed and updated (including conversion to past tense) for entry into the CSR after the analysis has taken place.

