2.6 Analysis of the primary objective

The primary objective of the study is to evaluate the efficacy of re-infusion of tisagenlecleucel for restoring B-cell aplasia as measured by the incidence of B-cell aplasia within 12 months following tisagenlecleucel re-infusion.

Where **loss of B-cell aplasia** (i.e. B-cell recovery) is defined as:

- PB absolute B lymphocyte count $\geq 50/\mu\text{L}$, OR
- Peripheral blood B lymphocyte $\geq 10\%$ of the total lymphocytes

And where **B-cell aplasia** is defined as:

- PB absolute B lymphocyte count $< 50/\mu\text{L}$

The primary analysis of the study was to be performed after all patients had completed the 12-month follow-up period or discontinued earlier. However, this study terminated early due a very low rate of enrollment, and only 5 out of a planned 54 patients were enrolled; the low sample size provides insufficient data to perform the planned statistical analyses (see [Section 4](#)). Therefore, the available study data will be listed only for the primary objective using Full Analysis Set.

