2.12 Interim analysis

No formal interim analysis was planned for this study. Interim analyses could have been performed half-yearly following study start as required for publication purposes; however, no interim analyses were actually required due to early termination of the study.

3 Sample size calculation

This study is an exploratory study to determine the safety and efficacy of tisagenlecleucel re-infusion with an early loss of B-cell aplasia. The primary efficacy variable is the proportion of patients who restore B-cell aplasia (as defined in [Section 2.6](#)) within 12 months following re-infusion.

Sample size was based on an exact test for single proportion to test the null hypothesis $H_0: p \leq 0.10$, where p is the proportion of patients recovering B-cell aplasia during 12 months. If the true rate $p \geq 0.25$, then with a one sided alpha level of 2.5% and at least 80% power, a minimum of 49 evaluable patients will be required for the study. Considering a drop-out rate of 10%, a total of approximately 54 patients will be enrolled into the study.

4 Change to protocol specified analyses

The HESTER Trial has enrolled 5 patients over the course of one year. Given this rate of enrollment, the ability to enroll the planned number of patients within a reasonable time period is no longer feasible. Therefore, after careful consideration, it was decided to close the trial. Data is not adequate to perform statistical analysis. All study data will be listed.

The decision to close the study is not based on any issues related to safety.

Primary endpoint updated by removing text “presence of CTL019 cells by qPCR in the peripheral blood” from B-cell aplasia definition.

5 Appendix

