5.4 Statistical models

Not applicable.

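### Does SAP 2.6.2 still promise an exact confidence interval for the primary proportion, and rest on an unsupported threshold of 10 responders, after the switch to listings only?

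*SAP*

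**What the plan says.** SAP Section 2.6.2 describes the abandoned test and its rejection rule in the conditional past. Between those two sentences, one stays in the future: the proportion restoring aplasia after "re-infusion with tisagenlecleucel will be presented together with an exact 95% Clopper-Pearson confidence interval (CI"). The section then gives a count, "The estimated number of patients who restore B-cell aplasia required to reject the null hypothesis", as 10, without saying out of how many, and refers to Section 5.4. Under the heading "5.4 Statistical models" there is only a statement that the section does not apply. The last paragraph of 2.6.2 says the primary analysis will not be carried out as planned and ends: "Data for the primary objective will be listed only".

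The other relevant places are:

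- SAP Section 1: "insufficient data to perform the planned statistical analyses so study data will be listed only".
- SAP Section 2.6: "only 5 out of a planned 54 patients were enrolled", so the primary data are listed on the Full Analysis Set (FAS).
- SAP Section 2.6.1: aplasia data are listed by patient.
- SAP Section 4: "Data is not adequate to perform statistical analysis. All study data will be listed".
- SAP Section 3: 49 evaluable patients, about 54 enrolled, null rate 0.10, alternative 0.25, one-sided 2.5%, power at least 80%.
- Protocol Section 5: "Approximately 54 subjects will be enrolled to allow 49 subjects treated".

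**The concern.** Read literally, 2.6.2 asks the programmer both to produce a proportion with an interval and to produce only a listing. The neighbouring verbs were converted for the closeout and this one was not, so it can be taken for a live instruction. The SAP also says it may seed the methods section of the study report, so a mistaken sentence has a route into that report.

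The bare count raises a separate doubt. A threshold for an exact test depends on the sample size, 10 responders cannot occur among 5 patients, and the place that should justify the number is empty. If 10 were wrong for the planned size, the stated error rate and power would be wrong too.

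**Working it through.** **Is the count of 10 right?**

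Inputs (SAP 2.6.2 and 3): p0 = 0.10, p1 = 0.25, one-sided alpha 0.025, n = 49. Reject if the lower limit of the exact 95% interval exceeds 0.10.

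Formulas: the lower limit L(x, n) is the 0.025 quantile of Beta(x, n − x + 1). Error and power are the binomial tails P(X ≥ r | n, p0) and P(X ≥ r | n, p1).

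| n | r | L(r, n) | one-sided error | power at 0.25 |
|---|---|---|---|---|
| 48 | 10 | 0.1047 | 0.0187 | 0.795 |
| 49 | 9 | 0.0876 | 0.0519 | 0.895 |
| 49 | 10 | 0.1024 | 0.0215 | 0.817 |
| 54 | 10 | 0.0925 | 0.0398 | 0.899 |
| 54 | 11 | 0.1063 | 0.0166 | 0.826 |

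At n = 49 the smallest rejecting count is 10, and 49 is the smallest n that reaches 80% power. Both planned figures reproduce. For enrolment, 49/0.9 = 54.4 and 54 × 0.9 = 48.6, consistent with about 54 enrolled for 49.

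**Does the missing denominator matter?** Ten is the minimum for n = 44 to 50; it is 9 for n = 40 to 43 and 11 for n = 51 to 57. The decision rule, however, is the interval limit, which adapts to whatever n occurs. The count only illustrates that rule at the planned size, and the size is stated in SAP Section 3.

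**What would the live sentence produce now?** The FAS size is not stated and is at most 5. If all 5 were re-infused (an assumption), the exact intervals would be:

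- 0/5: 0 to 52.2%
- 2/5: 5.3 to 85.3% (80 points wide)
- 3/5: 14.7 to 94.7%
- 5/5: 47.8 to 100%

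Such intervals tell a reader little that five listed patients do not.

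**Which instruction governs?** One unconverted verb stands against explicit, reasoned statements in five places (SAP 1, 2.6, 2.6.1, 4 and the end of 2.6.2). The supporting rules are also switched off: missing data (2.6.3), supportive analyses (2.6.4) and statistical models (5.4) are all marked not applicable. A plan that meant to keep the estimate would need at least the first of these. Future tense alone does not mark live work either, since SAP Section 3 keeps it for the abandoned enrolment target.

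**The case for a change.** The best case for a change starts from the SAP's own convention. Section 1 says the document is written in the future tense and will be turned into the past for the report. Converted mechanically, the sentence would state that an interval was presented when none was. The closing words of 2.6.2, that the analysis will not be done as planned, could also be read as dropping the test while keeping the estimate. On the count, the planned number quoted in SAP 2.6 is 54, where 10 responders would not reject. If drop-out meant loss after infusion, the FAS could approach 54, because Protocol 12.4.3 counts unknown responses as non-responders. At n = 5 the interval rule would be met by 3 of 5, which does not match a count of 10.

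The inconsistency is real: the verb was missed, and the pointer to Section 5.4 leads nowhere. The harm does not follow. The same passage of Section 1 promises review and updating as well as tense conversion, and the sentence that follows directly in 2.6.2 rules out anything beyond a listing. The reading with an FAS near 54 is possible in principle, but Protocol Section 5 ties the 54 enrolled to 49 treated, and the FAS is everyone re-infused. The mismatch at n = 5 concerns a test the plan has withdrawn.

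**Conclusion.** No change is needed. The section carries two editorial leftovers, one verb and one dead cross-reference, which anyone drafting the report text would correct in passing. The count of 10 is not an error; it belongs to the 49 evaluable patients of the original design. The effect on the trial's results is nil, because no hypothesis is tested and the primary data appear only as listings.

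Keeping a descriptive interval instead would bring no gain: it would run against the stated listing-only decision, would need a missing-data rule the plan has withdrawn, and could be about 80 points wide. The conclusion assumes that the listing-only decision is carried out as SAP Sections 1, 2.6, 2.6.1 and 4 describe, and that 49 is the planned number treated, as Protocol Section 5 says.

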2.6.3 Handling of missing values/censoring/discontinuations

Not applicable.

2.6.4 Supportive analyses

Not applicable.

2.6.4.1 Sensitivity analyses

Not applicable.

2.6.4.2 Subgroup analyses

Not applicable.

2.7 Analysis of the key secondary objective

There are no key secondary objectives for this study.

2.8 Analysis of secondary efficacy objectives

Note: The secondary efficacy analysis will not be performed as there is an inadequate number of patients in the study.

2.8.1 Secondary endpoints

Note: The secondary efficacy analysis will not be performed as there is an inadequate number of patients in the study.

2.8.1.1 Overall remission rate

Note: The secondary efficacy analysis will not be performed as there is an inadequate number of patients in the study.

2.9 Safety analyses

2.9.1 Adverse events

All AEs and SAEs data (including data from the pre re-infusion period) will be listed using Screened Set.

Treatment-emergent AEs (TEAEs) are defined as AEs that started or worsened after tisagenlecleucel re-infusion.

In addition, for the legal requirements of clinicaltrials.gov and EudraCT, two required tables on TEAEs which are not SAEs with an incidence greater than 5% and on treatment emergent SAEs and SAEs suspected to be related to tisagenlecleucel will be provided by primary SOC and PT using Safety Set.

If for the same patient, several consecutive AEs (irrespective of study treatment causality, seriousness and severity) occurred with the same primary SOC and PT:

- A single occurrence will be counted if there is ≤ 1 day gap between the end date of the preceding AE and the start date of the consecutive AE.
- More than one occurrence will be counted if there is > 1 day gap between the end date of the preceding AE and the start date of the consecutive AE. For occurrence, the presence of at least one SAE/SAE suspected to be related to tisagenlecleucel/non-SAE has to be checked in a block e.g., among AEs in a ≤ 1 day gap block, if at least one

SAE is occurring, then one occurrence is calculated for that SAE.

2.9.1.1 Deaths

Death data will be listed using the Screened Set.

2.9.1.2 Adverse events of special interest / grouping of adverse events

[figure not shown]
Not applicable.

2.9.1.3 Cytokine release syndrome

Cytokine release syndrome data will be listed using the Safety Set.

2.9.2 Laboratory data

Laboratory data will be listed for all patients in the Enrolled Set. Results will be graded by the low/normal/high classifications based on laboratory normal ranges.

2.9.3 Other safety data

Other safety data will be listed using the Enrolled Set.

2.9.3.1 Vital signs

Vital signs data will be listed.

2.9.3.2 Other safety assessments

Karnofsky/Lansky performance scores (100, 90, 80, 70, 60, 60, <50) will be listed.

[figure not shown]
All other safety data will be listed.

2.10 Pharmacokinetic endpoints

For all pharmacokinetic (PK) analyses, the Enrolled Set will be used, unless stated otherwise.

No inferential tests for PK analyses will be performed.

Tisagenlecleucel concentrations in peripheral blood will be measured by qPCR and listed by treatment, subject, and visit (D1 pre-dose, D28, M3 and M12) from Full Analysis Set. Concentrations below 10 copies/reaction (LLOQ) will be treated as zero. All unplanned PK results will be listed.

2.12 Interim analysis

No formal interim analysis was planned for this study. Interim analyses could have been performed half-yearly following study start as required for publication purposes; however, no interim analyses were actually required due to early termination of the study.

3 Sample size calculation

This study is an exploratory study to determine the safety and efficacy of tisagenlecleucel re-infusion with an early loss of B-cell aplasia. The primary efficacy variable is the proportion of patients who restore B-cell aplasia (as defined in [Section 2.6](#)) within 12 months following re-infusion.

Sample size was based on an exact test for single proportion to test the null hypothesis $H_0: p \leq 0.10$, where p is the proportion of patients recovering B-cell aplasia during 12 months. If the true rate $p \geq 0.25$, then with a one sided alpha level of 2.5% and at least 80% power, a minimum of 49 evaluable patients will be required for the study. Considering a drop-out rate of 10%, a total of approximately 54 patients will be enrolled into the study.

4 Change to protocol specified analyses

The HESTER Trial has enrolled 5 patients over the course of one year. Given this rate of enrollment, the ability to enroll the planned number of patients within a reasonable time period is no longer feasible. Therefore, after careful consideration, it was decided to close the trial. Data is not adequate to perform statistical analysis. All study data will be listed.

The decision to close the study is not based on any issues related to safety.

Primary endpoint updated by removing text “presence of CTL019 cells by qPCR in the peripheral blood” from B-cell aplasia definition.

5 Appendix

5.1 Imputation rules

Not applicable.

5.2 AEs coding/grading

Reporting of AEs will be based on MedDRA version 24.1 or higher and the CTCAE version 4.03 or higher. The grading of CRS will be based on study protocol specific grading scales. For the analysis purpose, the latest version of MedDRA available at analysis cut-off date will be used for reporting activity.

5.3 Laboratory parameters derivations

Not applicable.

5.4 Statistical models

Not applicable.

5.5 Visit windows

Not applicable.

